## **5.2. Subject Identification and Randomisation of Treatment**

### **5.2.1. Subject Identification**

Subject identification numbers will be assigned sequentially to the subjects who have consented to participate in the study, according to the range of subject identification numbers allocated to each study centre.

### **5.2.2. Randomisation of Treatment**

#### **5.2.2.1. Randomisation of Supplies**

The randomisation of supplies within blocks will be performed at GSK Biologicals using MATerial EXcellence (MATEX), a program developed for use in Statistical Analysis System (SAS®) (Cary, NC, USA) by GSK Biologicals. Entire blocks will be shipped to the study centres /warehouse(s).

To allow GSK Biologicals to take advantage of greater rates of recruitment than anticipated at individual centres in this multi-centre study and to thus reduce the overall study recruitment period, an over-randomisation of supplies will be prepared.

#### **5.2.2.2. Treatment Allocation to the Subject**

The treatment numbers will be allocated by dose.

##### **5.2.2.2.1. Study Group and Treatment Number Allocation**

The target will be to enrol approximately 800 eligible subjects who will be randomly assigned to one of the four study groups in a (1: 1: 1: 1) ratio (approximately 200 subjects in each group).

Allocation of the subject to a study group at the investigator site will be performed using a randomisation system on the Internet (SBIR). The randomisation algorithm will use a minimisation procedure accounting for centre, country and number of doses of *Prevenar 13* received before the study start (2 or 3 doses). Minimisation factors will have equal weight in the minimisation algorithm.

After obtaining the signed and dated ICF from the subject's parent(s)/LAR(s) and having checked the eligibility of the subject, the site staff in charge of the vaccine administration will access SBIR. Upon providing the subject identification number, the randomisation system will determine the study group and will provide the treatment number to be used for the first dose.

The number of each administered treatment must be recorded in the eCRF on the Vaccine Administration screen.

When SBIR is not available, please refer to the SBIR user guide or the Study Procedures Manual (SPM) for specific instructions.

##### **5.2.2.2.2. Treatment Number Allocation for Subsequent Doses**

For each dose subsequent to the first dose, the study staff in charge of the vaccine administration will access SBIR, provide the subject identification number, and the system will provide a treatment number consistent with the allocated study group.

The number of each administered treatment must be recorded in the eCRF on the Vaccine Administration screen.

#### **5.2.3. Allocation of Subjects to Assay Subsets**

[Table 4](#) presents the subsets which will be used for antibody determination.

**Table 4. Subsets (Amended 02 July 2014)**

Subset name	Description	Definition	Estimated number of subjects
Subset 1	Groups ACWY1d and ACWY2d: hSBA-MenA and hSBA-MenC	The first 50% of enrolled subjects within each country (according to their enrolment date) of groups ACWY1d and ACWY2d will be tested for hSBA-MenA and hSBA-MenC at all blood sampling timepoints planned for each group (i.e. Visits 1, 2, 5, 6 and 7 for the ACWY1d group and Visits 1, 2, 4, 5, 6 and 7 for the ACWY2d group).	200
Subset 2	Groups ACWY1d and ACWY2d: hSBA-MenW and hSBA-MenY	The remaining 50% of enrolled subjects within each country (according to their enrolment date) of groups ACWY1d and ACWY2d will be tested for hSBA-MenW-135 and hSBA-MenY at all blood sampling timepoints planned for each group (i.e. Visits 1, 2, 5, 6 and 7 for the ACWY1d group and Visits 1, 2, 4, 5, 6 and 7 for the ACWY2d group).	200
Subset 3	Groups Co-ad and PCV-13: OPA 3, 4, 6B, 14, 23F	The first 50% of enrolled subjects within each country (according to their enrolment date) of groups Co-ad and PCV-13 will be tested for OPA for pneumococcal serotypes 3, 4, 6B, 14 and 23F at Visits 1 and 2.	200
Subset 4	Groups Co-ad and PCV-13: OPA 1, 5, 6A, 7F, 9V, 18C, 19A, 19F	The remaining 50% of enrolled subjects within each country (according to their enrolment date) of groups Co-ad and PCV-13 will be tested for OPA for pneumococcal serotypes 1, 5, 6A, 7F, 9V, 18C, 19A and 19F at Visits 1 and 2.	200

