### **Overview of the Recruitment Plan**

Approximately 800 subjects will be enrolled in this study

In order to take advantage of greater rates of recruitment than anticipated in individual centres, an over-randomisation of approximately 20% will be prepared.

The duration of the study will be approximately 62 months per subject.

Recruitment is anticipated to take 6 months.

The actual number of subjects enrolled versus the target number of subjects will be assessed on a continuous basis utilising an internet-based randomisation system (SBIR).

Local personnel are responsible for monitoring and direct implementation of the recruitment plan.

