2. STUDY DESIGN

Enrolment of
800 toddlers

Randomisation
(1:1:1:1)

- **Experimental design:** Phase 3, open-label, randomized, controlled, multicenter study with 4 parallel vaccine groups.
- **Duration of the study:** 62 months for each subject:
 - Epoch 001: Primary starting at Visit 1 (Month 0) and ending at the phone contact (Month 9)
 - Epoch 002: Persistence Visit 5 ending Year 1
 - Epoch 003: Persistence Visit 6 ending Year 3
 - Epoch 004: Persistence Visit 7 ending Year 5
- **Control:** Active control.
- **Vaccine allocation:** Randomized.
- **Blinding:** Open-label.

- The subsets that are used for antibody titer determination are given below:

Subset name	Description	Definition
Subset 1	Vaccine groups ACWY1d and ACWY2d: hSBA-MenA and hSBA-MenC	The first 50% of enrolled subjects within each country (according to their enrollment date) for vaccine groups ACWY1d and ACWY2d will be tested for hSBA-MenA and hSBA-MenC at all blood sampling time points planned for each vaccine group (ie, Visits 1, 2, 5, 6, and 7 for the ACWY1d vaccine group and Visits 1, 2, 4, 5, 6, and 7 for the ACWY2d vaccine group).
Subset 2	Vaccine groups ACWY1d and ACWY2d: hSBA-MenW-135 and hSBA-MenY	The remaining 50% of enrolled subjects within each country (according to their enrollment date) for vaccine groups ACWY1d and ACWY2d will be tested for hSBA-MenW-135 and hSBA-MenY at all blood sampling time points planned for each vaccine group (ie, Visits 1, 2, 5, 6, and 7 for the ACWY1d vaccine group and Visits 1, 2, 4, 5, 6, and 7 for the ACWY2d vaccine group).
Subset 3	Vaccine groups Co-ad and PCV13: OPA 3, 4, 6B, 14, and 23F	The first 50% of enrolled subjects within each country (according to their enrollment date) for vaccine groups Co-ad and PCV13 will be tested for opsonophagocytic activity (OPA) for pneumococcal serotypes 3, 4, 6B, 14, and 23F at Visits 1 and 2.
Subset 4	Vaccine groups Co-ad and PCV13: OPA 1, 5, 6A, 7F, 9V, 18C, 19A, and 19F	The remaining 50% of enrolled subjects within each country (according to their enrollment date) for vaccine groups Co-ad and PCV13 will be tested for OPA for pneumococcal serotypes 1, 5, 6A, 7F, 9V, 18C, 19A, and 19F at Visits 1 and 2.

The following vaccine group names will be used for the statistical analyses:

Vaccine group order in tables	Vaccine group label in tables	Vaccine group definition for footnote	Pooled vaccine groups label in tables	Pooled definition for footnote

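### The hSBA and OPA subsets are chosen by enrolment order within country, so each panel's estimate for an arm rests on early or on late enrollees only

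*Protocol*

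**What the plan says.** Protocol section 5.2.3, Table 4, defines four assay subsets, all by date of entry within country.

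- **Subset 1, hSBA for MenA and MenC.** The table's definition reads: "The first 50% of enrolled subjects within each country (according to their enrolment date) of groups ACWY1d and ACWY2d will be tested for hSBA-MenA".
- **Subset 2, hSBA for MenW-135 and MenY.** Its definition reads: "The remaining 50% of enrolled subjects within each country (according to their enrolment date) of groups ACWY1d and ACWY2d will be tested for hSBA-MenW-135".
- **Subset 3, five OPA serotypes (3, 4, 6B, 14 and 23F).** Its definition reads: "The first 50% of enrolled subjects within each country (according to their enrolment date) of groups Co-ad and PCV-13 will be tested for OPA".
- **Subset 4, the other eight OPA serotypes.** Its definition reads: "The remaining 50% of enrolled subjects within each country (according to their enrolment date) of groups Co-ad and PCV-13 will be tested for OPA".

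SAP section 2 carries the same rule, for example "The remaining 50% of enrolled subjects within each country (according to their enrollment date) for vaccine groups ACWY1d and ACWY2d" for Subset 2. Protocol Table 11 refers back to section 5.2.3 for the method of selection and adds nothing.

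Neither document describes a random draw or gives a reason for using enrolment order. The Amendment 1 entry in the Document History explains which serotypes go into which OPA subset, but not how children are chosen. Minimisation (Protocol section 5.2.2.2.1) balances centre, country and prior Prevenar 13 doses across study groups; subset is not part of it. The recruitment plan in Protocol section 4.1 says: "Recruitment is anticipated to take 6 months".

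**The concern.** The secondary endpoints are stated for the arms: hSBA for all four serogroups at one month and at Years 1, 3 and 5, and OPA for all 13 serotypes at one month. A reader will take each figure as a description of the arm. Under Table 4, the MenA and MenC figures come only from children who entered in the first half of their country's recruitment, and the MenW-135 and MenY figures only from those who entered later. For hSBA this lasts to Visit 7, because the same children are retested.

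Over about six months of recruitment the two halves can differ in season of vaccination and in which centres were open. A centre that opens late in its country may contribute only to Subsets 2 and 4. If response drifts with any of this, each panel departs from its arm's value, and a larger sample would not correct it. The by-country hSBA and OPA tables (SAP sections 6.1.2.1 and 6.2.2.1) are the most exposed, because within one country the panels are divided entirely by entry order.

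**Working it through.** **1. Reproduce the subset sizes.** About 200 children per arm (Protocol section 5.2.2.2.1: "randomly assigned to one of the four study groups in a (1: 1: 1: 1) ratio (approximately 200 subjects in each group") and a 50% split over two arms give 0.5 × (200 + 200) = 200 per subset, as in Table 4, or 100 enrolled per arm and panel.

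For persistence, 640 evaluable children less 10% per visit (Protocol section 10.3), with one quarter in each hSBA subset:

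| Visit | Computed | Table 11 |
|---|---|---|
| Year 1 | 640 × 0.9 / 4 = 144.0 | 144 |
| Year 3 | 640 × 0.9² / 4 = 129.6 | 129 |
| Year 5 | 640 × 0.9³ / 4 = 116.6 | 117 |

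The plan's figures reproduce to within rounding.

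**2. Evaluable children per arm and panel.** Month 1: 160 evaluable per arm (Protocol section 10.3), so 160 / 2 = 80. Year 5 (hSBA only): 117 / 2 = 58.5, taken as 58.

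**3. Shift of a panel from the arm's value.** Let pE and pL be the proportions at or above the cut-off in early and late enrollees, with d = pE − pL. With equal halves the arm's value is (pE + pL)/2. A panel read only in early enrollees estimates pE, so its shift is pE − (pE + pL)/2 = d/2. A late panel is shifted by −d/2. If the same d applies to both panels, a contrast between them carries an extra d.

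The documents give no value for d. By assumption:

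| d (points) | Shift per panel | Added to a between-panel contrast |
|---|---|---|
| 0 | 0 | 0 |
| 5 | 2.5 | 5 |
| 10 | 5 | 10 |

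**4. Sampling error for scale.** SE = √(p(1 − p)/n), for p from 0.2 to 0.5.

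- Month 1, n = 80: √(0.16/80) = 4.5 points; √(0.25/80) = 5.6 points.
- Year 5, n = 58: √(0.16/58) = 5.3 points; √(0.25/58) = 6.6 points.

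At Month 1 the assumed shift is therefore between 2.5/5.6 = 0.4 and 5/4.5 = 1.1 standard errors.

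**5. Check by simulation.** 3,000 runs were made with 400 children in two arms, six countries of about equal size and a mean proportion of 80%. Selection by entry order shifted the panel by 0.0, 2.5 and 5.0 points at d = 0, 5 and 10. Random halves within country shifted it by at most 0.1 point. The mean difference between arms within the panel, with no true arm effect, was at most 0.1 point under entry order and 0.3 point under random halves, which is simulation noise.

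**6. Cost in precision of a random draw.** None: the panel sizes in steps 1 and 2 do not change.

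**The case against.** The strongest reply is that the planned comparisons are sound. ACWY2d against ACWY1d and Co-ad against PCV-13 (Protocol section 10.6.2.2, SAP section 6.1.2.2) are made serogroup by serogroup or serotype by serotype, and both arms follow the same subset rule. No planned analysis sets one panel against the other. The endpoints are secondary, Protocol section 10.8 makes their comparisons descriptive, and hSBA is openly described as measured in a subset. The split is made within country, entry age is fixed at 12 to 14 months and recruitment is short, so drift may be small. All of this stands. It limits the point to how well a panel represents its arm and to informal reading across panels.

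Three stronger inferences are tempting, and the documents do not support them.

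- **That serogroup is fully confounded with enrolment period.** MenA and MenC are read in the same children, as are MenW-135 and MenY, and the serotypes within each OPA panel. The mixing arises only between panels. Early and late are also relative to each country, so the halves can overlap in calendar time across the six countries listed in SAP section 2.
- **That South African HIV screening changed the population partway through.** The Document History says the authority wanted screening before enrolment in that country. No enrolment dates are given, and nothing shows that a South African child entered before the amendment.
- **That a drift of 5 to 10 points exists.** That range only illustrates scale; the documents contain no evidence on d.

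**Conclusion.** The point holds as a minor design weakness. All four subsets are filled by entry order without a stated reason, so each secondary hSBA or OPA estimate for an arm represents half of its enrolment period within each country. The possible shift is d/2 per panel: zero without drift, and 2.5 to 5 points for an assumed d of 5 to 10. That compares with a standard error of about 4.5 to 5.6 points at Month 1 and, for hSBA, about 5.3 to 6.6 points at Year 5. These figures assume equal halves, the protocol's drop-out rates and proportions of 0.2 to 0.5.

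The confirmatory objectives use rSBA and pneumococcal ELISA in all children of the relevant arms and are untouched. Comparisons between arms within a panel remain randomised.

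**What to change.** **Design.** In Protocol Table 4 and SAP section 2, replace the enrolment-date rule with a random 1:1 draw to Subset 1 or 2 (ACWY1d, ACWY2d) and to Subset 3 or 4 (Co-ad, PCV-13). SBIR should make the draw at allocation, stratified by arm and country and not shown to the site. The cost is one extra draw and a wording change; assay numbers and serum volume stay the same. Stratifying by arm also settles a gap in the current text, which does not say whether the 50% is counted within each arm or over the two arms together.

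**Samples already tested.** The SAP's Document History (version 3) records that the Month 0 to Month 9 analyses had been performed. A new draw at that stage would break the children's hSBA series, so keep the existing subsets and add:

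- a descriptive table by subset and arm of rSBA results (ACWY1d, ACWY2d) or pneumococcal ELISA results (Co-ad, PCV-13), with centre, enrolment month and prior Prevenar 13 doses;
- a statement in the SAP and the reports that panels should not be compared with each other.

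Protocol Table 11 shows that rSBA and ELISA are measured in all children of these arms at Visits 1 and 2, so the table needs no new assays. It should include GMTs and the 1:128 cut-off: Protocol Table 21 assumes 97.3% to 98.4% at 1:8 or above, which leaves little room for drift to show. Similar rSBA or ELISA results in the two halves would be reassuring but not proof, because hSBA and OPA are different assays.

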### 5.3. Method of Blinding

The study will be conducted in an open manner. The study cannot be double-blind due to differences in the external appearance of the vaccine vials and the difference in the vaccination schedules in each of the four study groups.

The laboratory in charge of the laboratory testing will be blinded to the treatment, and codes will be used to link the subject and study (without any link to the treatment attributed to the subject) to each sample.

### 5.4. General Study Aspects

Supplementary study conduct information not mandated to be present in this protocol is provided in the accompanying SPM. The SPM provides the investigator and the site personnel with administrative and detailed technical information that does not impact the safety of the subjects.

### 5.5. Outline of Study Procedures

An outline of the schedule of assessments to be performed in subjects during the course of the study is provided in [Table 5](#) for the ACWY1d and Co-ad groups and in [Table 6](#) for the ACWY2d and PCV-13 groups.

**CONFIDENTIAL**

C0921003 (MENACWY-TT-104,116892)

Protocol Amendment 3, 09 May 2018

# HIV rapid testing is mandatory only for subjects from South Africa, prior to their enrolment in the study. If source documentation shows that the subject is HIV negative based on previous testing at other facilities, no additional HIV rapid testing is needed, unless clinically indicated by the investigator. Refer to [Section 5.6.7](#). (Amended 02 July 2014).

 All vaccines administered since birth have to be recorded.

 Up to Visit 2, all non-study vaccines administered within 30 days preceding the study vaccine and any medications/non-study vaccinations taken on Days 0-30 following vaccination (day of vaccination is considered Day 0) will be recorded. Throughout the whole study, any investigational or non-registered medication or vaccine, any meningococcal vaccine, any pneumococcal vaccine and any medication to treat SAEs that are required to be reported per protocol will be recorded.

 These conditions include: any confirmed or suspected condition that has the capability of altering the subject's immune response (e.g. intercurrent lymphopenia, the occurrence of meningococcal or pneumococcal disease, any confirmed or suspected immunosuppressive or immunodeficient condition and diagnosis of serious chronic illness) throughout the study. Report using the Non-Serious Adverse Events and Intercurrent Medical Conditions eCRF form.

 Occurrences of meningococcal or pneumococcal diseases should be reported as SAEs and documented in the AE report in the eCRF.

 This will also include SAE(s) leading to the withdrawal of the subject from the study.

 In the event of Guillain-Barré Syndrome (GBS) subjects' parents/LARs should be contacted to obtain clinical details as outlined in the 'Potential immune mediated disorders: standard questionnaires and list of preferred terms'. All occurrences of GBS have to be reported as SAEs.

 New Onset of Chronic Illnesses (NOCIs) (e.g. auto-immune disorders, allergies, type 1 diabetes, asthma) will be recorded until the ESFU phone contact and will be reported either as an AE or as an SAE as appropriate.

 To be completed for all subjects who are enrolled in the study.

**CONFIDENTIAL**

C0921003 (MENACWY-TT-104,116892)

Protocol Amendment 3, 09 May 2018

**Table 6. List of study procedures for groups ACWY2d and PCV-13**

Age	12-14 months	13-15 months	14-16 months	15-17 months	21-23 months	26-28 months	50-52 months	74-76 months
Epoch	001					002	003	004
Type of contact	Visit 1	Visit 2	Visit 3	Visit 4	Phone contact	Visit 5	Visit 6	Visit 7
Timepoints	Month 0	Month 1	Month 2	Month 3	Month 9	Year 1	Year 3	Year 5
Sampling timepoints	Pre-Vacc	Month 1 Post-Vacc	Month 2 Post-Vacc	Month 3 Post-Vacc	ESFU	Y1 Post-Vacc	Y3 Post-Vacc	Y5 Post-Vacc
Informed consent	•							
Informed assent (according to local requirement)							X	X
Demography	•							
Informed consent for HIV testing # (Amended 02 July 2014)	O							
HIV testing # (Amended 02 July 2014)	O							
Inclusion/exclusion criteria	•							
Medical history	•							
Check medical history since last visit done							•	•
Vaccination history 	•							
Physical examination	O							
Check contraindications	O		O					
Check warnings and precautions	O		O					
Pre-vaccination body temperature	•		•					
Study group and treatment number allocation	O							
Treatment number allocation for subsequent doses			O					
Recording of administered treatment number	•		•					
Blood sampling for antibody determination (approx. 5 ml)	•	•		•		•	•	•
Vaccine administration: MenACWY-TT in group ACWY2d and Prevenar 13 in group PCV-13	•							

**CONFIDENTIAL**

C0921003 (MENACWY-TT-104,116892)

Protocol Amendment 3, 09 May 2018

**Table 6. List of study procedures for groups ACWY2d and PCV-13**

Age	12-14 months	13-15 months	14-16 months	15-17 months	21-23 months	26-28 months	50-52 months	74-76 months
Epoch	001					002	003	004
Type of contact	Visit 1	Visit 2	Visit 3	Visit 4	Phone contact	Visit 5	Visit 6	Visit 7
Timepoints	Month 0	Month 1	Month 2	Month 3	Month 9	Year 1	Year 3	Year 5
Sampling timepoints	Pre-Vacc	Month 1 Post-Vacc	Month 2 Post-Vacc	Month 3 Post-Vacc	ESFU	Y1 Post-Vacc	Y3 Post-Vacc	Y5 Post-Vacc
Vaccine administration (MenACWY-TT in groups ACWY2d and PCV13)			•					
Record timing related to reconstitution and vaccination of MenACWY-TT	• 		•					
Observation of subjects for 30 minutes after vaccination	O		O					
Record any concomitant medication/vaccination 	•	•	•	•	•	•	•	•
Record any intercurrent medical conditions 		•	•	•	•	•	•	•
Distribution of diary cards	O		O					
Recording of solicited adverse events (Days 0–3)	•		•					
Recording of non-serious adverse events within 30 days post-vaccination	•	•	•	•				
Return of diary cards		O		O				
Diary card transcription by investigator		O		O				
Recording of serious adverse events 	•	•	•	•	•			
Recording of SAEs related to study vaccine administration and any event related to lack of vaccine efficacy 	•	•	•	•	•	•	•	•
Recording of SAEs related to study participation 	•	•	•	•	•	•	•	•
Reporting of Guillain-Barré syndrome 	•	•	•	•	•			

**Table 6. List of study procedures for groups ACWY2d and PCV-13**

Age	12-14 months	13-15 months	14-16 months	15-17 months	21-23 months	26-28 months	50-52 months	74-76 months
Epoch	001					002	003	004
Type of contact	Visit 1	Visit 2	Visit 3	Visit 4	Phone contact	Visit 5	Visit 6	Visit 7
Timepoints	Month 0	Month 1	Month 2	Month 3	Month 9	Year 1	Year 3	Year 5
Sampling timepoints	Pre-Vacc	Month 1 Post-Vacc	Month 2 Post-Vacc	Month 3 Post-Vacc	ESFU	Y1 Post-Vacc	Y3 Post-Vacc	Y5 Post-Vacc
Reporting of New Onset of Chronic Illnesses 	●	●	●	●	●			
Study Conclusion 								●

Note: The double-line border following Month 3 and 9 and Year 1 and 3 indicates the analyses which will be performed on all data (i.e. data that are as clean as possible) obtained up to Month 3 and 9 and Year 1 and 3.

Vacc: vaccination, ESFU: Extended Safety Follow-Up.

● is used to indicate a study procedure that requires documentation in the individual eCRF.

○ is used to indicate a study procedure that does not require documentation in the individual eCRF.

X Informed assent: as applicable according to local requirement, verbal or signed informed assent should be obtained at Visit 6 or Visit 7.

# HIV rapid testing is mandatory only for subjects from South Africa, prior to their enrolment in the study. If source documentation shows that the subject is HIV negative based on previous testing at other facilities, no additional HIV rapid testing is needed, unless clinically indicated by the investigator. Refer to [Section 5.6.7](#). (Amended 02 July 2014).

 All vaccines administered since birth have to be recorded.

 Only for group ACWY2d.

 Up to Visit 4, all non-study vaccines administered during the period starting 30 days preceding the first dose of study vaccine and ending 30 days after the last dose of study vaccine and any medications taken from the day of each vaccination until 30 days later will be recorded. Throughout the whole study, any investigational or non-registered medication or vaccine, any meningococcal vaccine, any pneumococcal vaccine and any medication to treat SAEs that are required to be reported per protocol will be recorded.

 These conditions include: any confirmed or suspected condition that has the capability of altering the subject's immune response (e.g. intercurrent lymphopenia, the occurrence of meningococcal or pneumococcal disease, any confirmed or suspected immunosuppressive or immunodeficient condition and diagnosis of serious chronic illness) throughout the study. Report using the Non-Serious Adverse Events and Intercurrent Medical Conditions eCRF form.

 Occurrences of meningococcal or pneumococcal diseases should be reported as SAEs and documented in the AE report in the eCRF.

 This will also include SAE(s) leading to the withdrawal of the subject from the study.

 In the event of Guillain-Barré Syndrome (GBS) subjects' parents/LARs should be contacted to obtain clinical details as outlined in the 'Potential immune mediated disorders: standard questionnaires and list of preferred terms'. All occurrences of GBS have to be reported as SAEs.

 New Onset of Chronic Illnesses (NOCIs) (e.g. auto-immune disorders, allergies, type 1 diabetes, asthma) will be recorded until the ESFU phone contact and will be reported either as an AE or as an SAE as appropriate.

 To be completed for all subjects who are enrolled in the study.

